### **11.4.3 Physical examination**

A listing of abnormal physical examination findings will be provided; no summaries of physical examination findings are planned.

#### **11.4.4 Neurological examination**

A listing of abnormal neurological examination findings will be provided; no summaries of neurological examination findings are planned.

#### **11.4.5 Psychiatric and mental status**

A listing of abnormal Psychiatric and Mental Status findings will be provided; no summaries of Psychiatric and Mental Status findings are planned.

#### **11.4.6 HADS**

The scoring algorithm for HADS is described in Section 3.8.3.

During the first 2 years, HADS was assessed at Month 2, Month 6, Month 12, Month 18, and Month 24 and at EDV for subjects who discontinued the study prior to the YEV at the end of the second year for all subjects, and was also assessed at Month 4 and Month 9 for some subjects from N01114. HADS was not assessed for subjects from N01187 and N01236. Prior to integrated protocol amendment 25, HADS was being assessed for time points beyond the YEV at the end of the second year. These additional assessments will not be summarized but will be provided in subject data listings.

[figure not shown]
Observed values for HADS depression and anxiety scores will be summarized for Baseline and Last Value for the Safety Analysis Set. Additionally, observed values will be summarized for Baseline and by visit for each study visit cohort. Change from Baseline will be summarized at each visit during the Evaluation Period.

For summaries of observed values at each time point, only subjects with a change from Baseline value at that time point will be summarized. Additionally, the mean and SD for each Baseline score will be provided at each post-Baseline time point for subjects included in the summary of change from Baseline.

#### **11.4.7 Columbia-Suicide Severity Rating Scale**

With global amendment 2 to the protocol, the Columbia-Suicide Severity Rating Scale (C-SSRS) was added as an assessment at all study visits. Specific rules are provided to the study sites with regard to the identification of AEs or SAEs based on the outcome of this assessment. Because clinical events of interest will be recorded as AEs or SAEs, no study variable is defined for this assessment and no analyses are planned for the C-SSRS within the context of this study. However, subject data listings of the data for the C-SSRS will be provided. Additional listings will be provided for the subset of subjects with suicidal ideation and the subset of subject with actual suicide attempts.

Suicide ideation includes a “yes” answer to any 1 of the 5 suicidal ideation questions:

Suicide attempt includes response of a “yes” answer to any 1 of the 3 suicide attempt questions:

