- ⁽ⁱ⁾ End of study status will be completed at the FV for subjects having performed an EDV (discontinued subjects) and for subjects leaving the study at the end of the program (completed subjects).
- ^(j) The C-SSRS assessment will be implemented by site per IRB/IEC approval upon completion of required training. As of the time of Protocol Amendment 2, all subjects had completed their EV. Thus, the C-SSRS was not assessed for any subjects at their EV.
- ^(k) Procedures only performed during the first 2 years of subject participation in the study or EDV/FV in case the subject discontinues participation within the first 2 years.
- ^(l) For subjects that may transition to another BRV study or a managed access program or similar type of program, the EDV will need to be completed, however down-titration and FV may not be applicable.

This document cannot be used to support any marketing applications and all dimensions or variations thereof.

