11.1.16 Adverse Events (AEs)

At the EV, the Investigator will record any AE that was still ongoing at the end of the previous study in the source documentation. From the EV onwards, adverse events will be assessed at each visit and recorded in the CRF and in the source documents. The study participant will be given the opportunity to report AEs spontaneously. A general prompt will also be given to detect AEs, e.g., “Did you notice anything unusual about your health (since your last visit)?” In addition, the Investigator should review any self-assessment procedures (e.g. DRCs) used in the study.

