#### *Overall Incidence Summaries*

- Incidence of TEAEs
- Incidence of TEAEs by 3-month time interval
- Incidence of TEAEs by study period (Evaluation, Down-Titration, Post-Treatment)
- Incidence of TEAEs for TEAEs occurring in at least 5% of subjects
- Incidence of TEAEs by 3-month time intervals for TEAEs occurring in at least 5% of subjects overall
- Incidence of non-serious TEAEs occurring in at least 5% of subjects

The incidence of TEAEs occurring in at least 5% of subjects will be summarized overall as noted above and also by subgroup for geographic region.

A subject is included in a 3-month interval if the subject was receiving BRV at any time during that interval based on their duration of exposure to BRV (eg, a subject with exposure for 91 days is included in the time interval for Months 1-3 and Months 4-6). Summaries of AEs by 3-month intervals will include all subjects who are classified into each time interval as defined above. TEAEs which had onset prior to or on the date of the last dose of BRV (or the date of last scheduled or unscheduled visit for subjects who are ongoing at the time of the clinical cutoff) are included in summaries by 3-month time intervals.

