### *TEAEs of interest*

AEs of interest will be identified based on MedDRA search criteria, which are documented outside of the SAP. The following summaries will be provided for AEs of interest:

- Incidence of TEAEs of interest
- Incidence of TEAEs of interest by 3-month time interval

For the summary by maximum intensity, each subject will be counted at most once per SOC or PT according to the maximum intensity of all AEs within that SOC or PT. Severe intensity will be assumed for AEs for which intensity is not specified.

Drug-related AEs are AEs for which the relationship to study drug is specified as Related or AEs for which relationship is not specified.

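### C-SSRS began only after every subject had entered, so a time trend in suicidality AEs cannot be separated from the later start of structured screening

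*SAP*

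**What the plan says.** On the instrument, SAP 11.4.7 says the C-SSRS was added with amendment 2. It continues: "Specific rules are provided to the study sites with regard to the identification of AEs or SAEs based on the outcome of this assessment". It then says "Because clinical events of interest will be recorded as AEs or SAEs, no study variable is defined for this assessment". The scale gets no analysis of its own; listings are planned for all C-SSRS data, for subjects with ideation and for subjects with attempts.

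On timing, footnote (j) to Protocol Table 5:1 states "As of the time of Protocol Amendment 2, all subjects had completed their EV", so no subject was assessed at entry. Roll-out was staggered: "The C-SSRS assessment will be implemented by site per IRB/IEC approval upon completion of required training".

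On AE collection in general, Protocol 11.1.16 relies on spontaneous reports, on a prompt ("A general prompt will also be given to detect AEs") and on investigator review of self-assessment records such as the Daily Record Card.

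On the tables, SAP 11.2.2 lists "Incidence of TEAEs by 3-month time interval" and "Incidence of TEAEs of interest by 3-month time interval". SAP 3.2.5 counts the intervals from the first BRV dose, and SAP 11.2.1 classifies AEs by onset date. Neither section separates time before the first C-SSRS from time after it, and no caveat is attached.

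**The concern.** The way suicidality is found changes part-way through the study, and the change lines up with the axis on which the tables are read. Every subject starts BRV without the C-SSRS; those who stay long enough acquire it later. The SAP's reason for not analysing the scale is that the AE record will carry the relevant events. That record is filled with the help of C-SSRS rules only in the later part of each subject's time.

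Long-term safety is the primary objective, and TEAEs, SAEs and withdrawal due to AE are the primary variables. A few suicidality AEs in late intervals against fewer in early ones could be taken as a risk emerging with long exposure when it reflects better detection. The overall incidence has a related weakness, because it mixes subject-time under two levels of detection.

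**Working it through.** The plan states no figure to reproduce: the study is descriptive and no sample size was calculated.

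**Inputs from the documents.** 108 subjects enrolled (SAP 2.4). The lag from entry to first C-SSRS is above zero for all. A subject counts in an AE interval if the last dose is on or after its first day (SAP 3.2.5). Post-entry visits are at Months 1, 2, 3, 6, 9, 12 and so on (Protocol Table 5:2).

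**Not in the documents, so assumed.** Accrual period, date of Amendment 2, dropout, true event rate and detection with and without the scale. One start date is used for all sites, although roll-out was staggered.

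**Step 1: coverage.** Let s be the study month in which a subject's C-SSRS starts. For an interval from month a to a+3, coverage is the mean over subjects of max(0, min(3, a+3−s))/3. With entry uniform over E months and the scale starting L months after the last entry, s is uniform on (L, L+E).

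- Fastest case (E = 12, L = 3), Months 10-12: (6 + 1.5)/12 = 62%. Months 25-27: 100%.
- Slowest case (E = 24, L = 24), Months 10-12: 0%. Months 25-27: 1.5/24 = 6%. Months 37-39: (12 + 1.5)/24 = 56%.
- Months 1-3: 0% whenever L is 3 or more. With L = 0 it is 1.5/24 = 6% to 1.5/12 = 12%.

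If dropout is unrelated to the lag, coverage cannot fall with time on BRV.

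**Step 2: effect on a constant true rate.** If screening finds R times as many events, the recorded rate relative to no screening is 1 + c(R − 1) at coverage c. With R = 2 assumed, the fastest case gives 1.62 at Months 10-12 and 2.00 at Months 25-27. The slowest gives 1.00 through Month 24, 1.06 at Months 25-27 and 1.56 at Months 37-39. The full factor appears only if coverage goes from 0% to 100%.

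**Step 3: can other mechanisms change the trend?** I simulated 400,000 subjects with 18-month accrual and, except where noted, median time on BRV of 18 months. True risk was 20 per 1000 per 3 months, constant unless noted. Each subject has at most one event. The gap is months from last entry to C-SSRS start.

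| Scenario (detection before → after C-SSRS) | Recorded per 1000, Months 1-3 → 22-24 |
|---|---|
| Complete detection throughout | 18.6 → 16.1 |
| 0.3 → 1.0, gap 0 | 6.8 → 16.6 |
| 0.3 → 1.0, gap 6, half of missed events back-dated | 9.7 → 16.3 |
| 0.8 → 1.0, gap 6 | 15.0 → 16.2 |
| 0.3 → 1.0, gap 36 | 5.5 → 5.0 (4.2 by Months 34-36) |
| 0.3 → 1.0, gap 6, all missed events back-dated, no dropout | 19.6 → 16.9 |
| 0.3 → 1.0, gap 6, true risk halving every 6 months | 4.8 → 1.3 |

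The first row falls slightly because subjects who have had their one event stay in the denominator. The second row is a rise of 16.6/6.8 = 2.4-fold. Step 2 agrees: R = 1/0.3 = 3.33 and coverage going from 0.08 to 1.00 give 3.33/1.19 = 2.8, and 2.8 × (16.1/18.6) = 2.4.

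In the last row the table falls, yet the distortion is still upward. Recorded incidence drops to 1.3/4.8 = 0.27 of its starting value, against a true 0.5^(21/6) = 0.09.

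**Step 4: counts.** With interval sizes assumed to fall from 108 to 48, coverage from 0 to 0.92, detection 0.3 → 1.0 and a constant true rate of 5 to 20 per 1000 per interval, about 1.5 to 6 recorded events are expected over 24 months. The second year shows the higher rate in 53% to 81% of replicates. If all 108 are in the Safety Analysis Set, a term needs 6 subjects (0.05 × 108 = 5.4) to enter the 5% tables, so these terms would probably appear only in the full interval table. Whether they are TEAEs of interest depends on criteria held outside the SAP.

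**The case against.** A reader might infer that suicidality AEs must rise with time on BRV by design. The documents do not support that; what is built in is rising C-SSRS coverage. Several features pull the other way:

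- Protocol 9.3 requires withdrawal after some positive answers, which removes higher-risk subjects from later intervals. The simulation did not include this.
- There are three scheduled visits in Months 1-3 and one per 3 months afterwards, so the general prompt is most frequent early.
- The Already Enrolled Subjects form looks back to study start. Since AEs are classified by onset, recalled events can fall in early intervals.

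A reader might also take the early period as unscreened. It was not: besides the prompt, Daily Record Cards were reviewed, psychiatric and behavioural symptoms were recorded at neurological examinations (Protocol 11.1.12), and HADS was completed in the first 2 years. None of these is a structured suicidality assessment, but together they could make earlier detection fairly high.

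It is also fair to say that the SAP tests nothing and prescribes no trend reading, and that 108 subjects can be reviewed case by case from the planned listings.

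These points limit what can be said about direction and size. They do not restore comparability across intervals. Only complete, correctly dated recall would close the detection gap, and nothing in the documents supports assuming it. Listings show cases but give no rate with a denominator of screened time.

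**Conclusion.** The point holds as a matter of confounding: in the 3-month tables, time on BRV and the start of structured screening cannot be separated for suicidality terms. The likely bias is upward in later intervals. Its size and even its direction depend on the unstated date of Amendment 2, on detection beforehand, on back-dating of onsets and on mandatory withdrawal of some positive subjects.

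The 2.4-fold rise illustrates one set of assumptions and is not an estimate for this study. A rise by the whole detection factor does not follow in general; with the slowest assumed roll-out and R = 2, the rate is unchanged for two years and 1.56-fold by Months 37-39. Because few events are expected, the practical risk is misreading a handful of late cases. The change is worth making because it is cheap and the outcome is serious.

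**What to change.** Amend SAP 11.2.2 and 11.4.7 as follows.

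1. Footnote the TEAE tables by 3-month interval: C-SSRS screening began after all subjects had entered, so suicidality terms must not be read as a time trend.
2. List the suicidality preferred terms. Tabulate them descriptively as events per 100 subject-years, separately for each subject's time before and after the first C-SSRS. Subjects never assessed contribute only to the earlier era. Where the data allow, mark events first identified through the look-back form.
3. Give the number and percentage of subjects with ideation and with attempts on the Since Last Visit form, among subjects with at least 1 such assessment. SAP 11.4.7 already defines both outcomes.
4. State the limits beside the tables. Counts per era are small. Amendment 2 also raised the maximum dose from 150 to 200 mg/day (SAP 2.3). The later era contains only subjects still in the study. The comparison is therefore descriptive and does not isolate the effect of screening.

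The cost is SAP wording and two small tables. They need the first C-SSRS date, C-SSRS responses, AE onset dates and dosing dates, and no new data collection.

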### 13 APPENDICES

#### 13.1 QOLIE-31-P Total and Subscale Score Calculations

The following outlines the calculation of the subscale scores for the QOLIE 31 P. The rescaled responses are provided for each item. The subscale scores are calculated by summing the rescaled responses for that subscale and dividing by the number of items with a non missing response. Note that the divisors shown assume that all items for each subscale have a response; the divisor will differ if there are missing responses. A subscale score will be calculated only if at least 50% of the items within the subscale are present.

| Scale/Item Numbers             | Response                     |      |      |     |    |     | Subtotal | Final Score
0-100 point scale |  |
|--------------------------------|------------------------------|------|------|-----|----|-----|----------|----------------------------------|--|
|                                | 1                            | 2    | 3    | 4   | 5  | 6   |          |                                  |  |
| Seizure Worry           |                              |      |      |     |    |     |          |                                  |  |
| 30.                            | 0                            | 20   | 40   | 60  | 80 | 100 | _____    |                                  |  |
| 31.                            | 0                            | 33.3 | 66.7 | 100 | —  | —   | _____    |                                  |  |
| 32.                            | 0                            | 50   | 100  |     | —  | —   | _____    |                                  |  |
| 33.                            | 0                            | 33.3 | 66.7 | 100 | —  | —   | _____    |                                  |  |
| 34.                            | 100                          | 75   | 50   | 25  | 0  | —   | _____    |                                  |  |
|                                |                              |      |      |     |    |     | TOTAL :  | _____ ÷ 5 = _____                |  |
| Overall Quality of Life |                              |      |      |     |    |     |          |                                  |  |
| 1.                             | Multiply each response by 10 |      |      |     |    |     |          |                                  |  |
| 36.                            | 100                          | 75   | 50   | 25  | 0  | —   | _____    |                                  |  |
|                                |                              |      |      |     |    |     | TOTAL :  | _____ ÷ 2 = _____                |  |
| Emotional Well-Being    |                              |      |      |     |    |     |          |                                  |  |
| 7.                             | 0                            | 20   | 40   | 60  | 80 | 100 | _____    |                                  |  |
| 8.                             | 0                            | 20   | 40   | 60  | 80 | 100 | _____    |                                  |  |
| 9.                             | 100                          | 80   | 60   | 40  | 20 | 0   | _____    |                                  |  |
| 10.                            | 0                            | 20   | 40   | 60  | 80 | 100 | _____    |                                  |  |
| 11.                            | 100                          | 80   | 60   | 40  | 20 | 0   | _____    |                                  |  |
|                                |                              |      |      |     |    |     | TOTAL :  | _____ ÷ 5 = _____                |  |
| Energy/Fatigue          |                              |      |      |     |    |     |          |                                  |  |
| 2.                             | 100                          | 80   | 60   | 40  | 20 | 0   | _____    |                                  |  |
| 3.                             | 100                          | 80   | 60   | 40  | 20 | 0   | _____    |                                  |  |
| 4.                             | 0                            | 20   | 40   | 60  | 80 | 100 | _____    |                                  |  |
| 5.                             | 0                            | 20   | 40   | 60  | 80 | 100 | _____    |                                  |  |
|                                |                              |      |      |     |    |     | TOTAL :  | _____ ÷ 4 = _____                |  |
| Cognitive Functioning   |                              |      |      |     |    |     |          |                                  |  |
| 19.                            | 0                            | 20   | 40   | 60  | 80 | 100 | _____    |                                  |  |
| 20.                            | 0                            | 33.3 | 66.7 | 100 | —  | —   | _____    |                                  |  |
| 21.                            | 0                            | 20   | 40   | 60  | 80 | 100 | _____    |                                  |  |
| 22.                            | 0                            | 20   | 40   | 60  | 80 | 100 | _____    |                                  |  |
| 23.                            | 0                            | 20   | 40   | 60  | 80 | 100 | _____    |                                  |  |
| 24.                            | 100                          | 75   | 50   | 25  | 0  | —   | _____    |                                  |  |
|                                |                              |      |      |     |    |     | TOTAL :  | _____ ÷ 6 = _____                |  |

**Medication Effects**

|     |     |      |      |     |   |   |       |
|-----|-----|------|------|-----|---|---|-------|
| 28. | 0   | 33.3 | 66.7 | 100 | — | — | _____ |
| 26. | 100 | 75   | 50   | 25  | 0 | — | _____ |
| 27. | 100 | 75   | 50   | 25  | 0 | — | _____ |

TOTAL : \_\_\_\_\_ ÷ 3 = \_\_\_\_\_

**Daily Activities/Social Functioning**

|     |     |    |    |    |     |     |       |
|-----|-----|----|----|----|-----|-----|-------|
| 13. | 0   | 20 | 40 | 60 | 80  | 100 | _____ |
| 14. | 0   | 25 | 50 | 75 | 100 | —   | _____ |
| 15. | 0   | 25 | 50 | 75 | 100 | —   | _____ |
| 16. | 100 | 75 | 50 | 25 | 0   | —   | _____ |
| 17. | 100 | 75 | 50 | 25 | 0   | —   | _____ |

TOTAL : \_\_\_\_\_ ÷ 5 = \_\_\_\_\_

Total score is calculated as a weighted sum of the subscale scores based on the weighting shown below. Total score will be missing if at least 1 subscale score is missing. Total score will range from 0 to 100 with a higher score reflecting better functioning.

| QOLIE-31-P Scale                            | Final Scale Score | Weight | Subtotal |
|--|--------------------------|---------------|-----------------|
| Seizure worry (a)                                  | _____                    | × 0.08        | = _____         |
| Overall quality of life (b)                        | _____                    | × 0.14        | = _____         |
| Emotional well-being (c)                           | _____                    | × 0.15        | = _____         |
| Energy/fatigue (d)                                 | _____                    | × 0.12        | = _____         |
| Cognitive functioning (e)                          | _____                    | × 0.27        | = _____         |
| Medication effects (f)                             | _____                    | × 0.03        | = _____         |
| Daily activities/Social functioning (g)            | _____                    | × 0.21        | = _____         |
| TOTAL SCORE : Sum subtotals (a) through (g) |                          |               | _____           |

### 13.2 Subject site transfers

| CRF# | Initial Site Subject # | Transfer Site Subject # |
|------|------------------------|-------------------------|
|      |                        |                         |

This document cannot be used to support any marketing authorization application and any extensions or variations thereof.

REDACTED COPY

### 13.3 PCST criteria

#### 13.3.1 Hematology parameters

| Parameter              | UCB Conventional Units  | SI Units  | CF  |
|------------------------|---|---|---|
| Hematocrit             | For 1 m to < 6 m: ≤ 25%
For 6 m to < 2 y: ≤ 27%
For 2 y to < 4 y: ≤ 29%
For 4 y to < 12 y: ≤ 32% (Female[F]); ≤ 35% (Male [M])
For ≥ 12 y: ≤ 32% (F); ≤ 37% (M)   | For 1 m to < 6 m: ≤ 0.25
For 6 m to < 2 y: ≤ 0.27
For 2 y to < 4 y: ≤ 0.29
For 4 y to < 12 y: ≤ 0.32 (F); ≤ 0.35 (M)
For ≥ 12 y: ≤ 0.32 (F); ≤ 0.37 (M)   | 0.01  |
| Hemoglobin             | For < 6 m: ≤ 9.7 g/dL
For 6 m to < 12 y: ≤ 10.0 g/dL
For ≥ 12 y: ≤ 9.5 g/dL (F); ≤ 11.5 g/dL (M)  | For < 6 m: ≤ 97 g/L
For 6 m to < 12 y: ≤ 100 g/L
For ≥ 12 y: ≤ 95 g/L (F); ≤ 115 g/L (M)  | 10  |
| Platelets              | ≤ 75 x 10  /L or ≥ 700 x 10  /L   | ≤ 75 x 10  /L or ≥ 700 x 10  /L   | Not applicable (N/A)  |
| White Blood Cell (WBC) | For < 17 y: ≤ 3.0 x 10  /L or ≥ 20 x 10  /L;
For ≥ 17 y: ≤ 2.8 x 10  /L or ≥ 16 x 10  /L;  | For < 17 y: ≤ 3.0 x 10  /L or ≥ 20 x 10  /L;
For ≥ 17 y: ≤ 2.8 x 10  /L or ≥ 16 x 10  /L;  | N/A   |
| Red Blood Cell (RBC)   | For < 17 y: ≤ 2.5 x 10  /mm 
For ≥ 17 y: ≤ 2.0 x 10  /mm  (F); ≤ 2.5 x 10  /mm  (M)  | For < 17 y: ≤ 2.5 x 10  /L
For ≥ 17 y: ≤ 2.0 x 10  /L (F); ≤ 2.5 x 10  /L (M)   | 1   |
| Eosinophils            | ≥ 10% or ≥ 0.7 x 10  /L   | ≥ 0.10 or ≥ 0.7 x 10  /L  | 0.01 or N/A   |
| Neutrophils            | ≤ 15% or ≤ 1.0 x 10  /L   | ≤ 0.15 or ≤ 1.0 x 10  /L  | 0.01 or N/A   |
| Basophils              | ≥ 5% or ≥ 0.4 x 10  /L  | ≥ 0.05 or ≥ 0.4 x 10  /L  | 0.01 or N/A   |
| Monocytes              | ≥ 20% or ≥ 1.5 x 10  /L   | ≥ 0.20 or ≥ 1.5 x 10  /L  | 0.01 or N/A   |
| Lymphocytes            | For 1 m to < 6 m: ≤ 22% or ≥ 80%
≤ 2.1 x 10  /L or ≥ 8.5 x 10  /L
For 6 m to < 2 y: ≤ 15% or ≥ 80%
≤ 1.5 x 10  /L or ≥ 7.5 x 10  /L
For 2 y to < 12 y: ≤ 12% or ≥ 80%
≤ 1.0 x 10  /L or ≥ 7.5 x 10  /L
For 12 y to < 17 y: ≤ 10% or ≥ 80%
≤ 0.5 x 10  /L or ≥ 5.5 x 10  /L
For ≥ 17 y: ≤ 10% or ≥ 80%
≤ 0.5 x 10  /L or ≥ 4.5 x 10  /L | For 1 m to < 6 m: ≤ 0.22 or ≥ 0.80
≤ 2.1 x 10  /L or ≥ 8.5 x 10  /L
For 6 m to < 2 y: ≤ 0.15 or ≥ 0.80
≤ 1.5 x 10  /L or ≥ 7.5 x 10  /L
For 2 y to < 12 y: ≤ 0.12 or ≥ 0.80
≤ 1.0 x 10  /L or ≥ 7.5 x 10  /L
For 12 y to < 17 y: ≤ 0.10 or ≥ 0.80
≤ 0.5 x 10  /L or ≥ 5.5 x 10  /L
For ≥ 17 y: ≤ 0.10 or ≥ 0.80
≤ 0.5 x 10  /L or ≥ 4.5 x 10  /L | 0.01
N/A
0.01
N/A
0.01
N/A
0.01
N/A
0.01
N/A |

